| CPX-POM infusions ²⁴ | | X | X | X | X | X | | | | |

Abbreviations: ALP = alkaline phosphatase; ALT = alanine aminotransferase; aPTT = activated partial thromboplastin time; AST = aspartate aminotransferase; BSA = body surface area; BUN = blood urea nitrogen; CPX-POM = ciclopirox phosphoryloxymethyl ester; CT = computed tomography; D = day; ECG = electrocardiogram; ECOG = Eastern Cooperative Oncology Group; EDTA = ethylenediamine tetraacetic acid; eGFR = estimated glomerular filtration rate; GGT = gamma glutamyl transferase; HIV = human immunodeficiency virus; IV = intravenous; MUGA = multi-gated acquisition; MRI = magnetic resonance imaging; PBMC = peripheral blood mononuclear cell; PD = pharmacodynamic; PK = pharmacokinetic; PT = prothrombin time; RBC = red blood cell; T3 = triiodothyronine; T4 = thyroxine; TSH = thyroid stimulating hormone; V = visit; WBC = white blood cell.

1. On Days 1 and 5 of Cycle 1, patients will be required to stay at the clinical research unit for at least 12 hours for PK sampling and other assessments. If patients are unable or unwilling to attend the required 12 hours of clinic visitation required for steady-state PK sampling on Day 5 of Cycle 1, the steady-state PK sampling may be postponed to Day 5 of Cycle 2. To shorten the duration of the Cycle 1, Day 1 visit, if needed, the safety laboratory blood samples required for this visit may be drawn up to 3 days before Day 1.
2. The Day 10 (Visit 8) study visit will only be required during Cycle 1.
3. After cycle 1; visit windows can be considered on a case by case basis due to events such as holidays; Cycle 1 needs to occur without visit windows. D6 can occur +2 calendar days for cycles after Cycle 1 is completed.
4. If final treatment cycle, patient returns for assessments on Day 22. If additional cycles are planned, patient skips this visit and restarts schedule at Day 1 (except for PK). Patients may continue to receive cycles of CPX-POM until progression of disease, intolerable toxicity occurs, or another withdrawal criterion applies.

5. The Follow-up visit will occur 28±5 days after the last dose of CPX-POM administered during the last treatment cycle. Or, in the event that a patient discontinues from the study prematurely, the site will make every effort to perform the assessments listed for this study visit.
6. Hepatitis screening will include tests for Hepatitis A, Hepatitis B, and Hepatitis C.

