7. Pregnancy tests will be required only for women of child bearing potential at Screening and before dosing on Day 1 of each treatment cycle. Urine or serum pregnancy tests are acceptable.
8. Cancer evaluation will include determination of staging and metastases for screening purposes (see Section 8.1). Disease response assessments will be performed for patients with measurable disease within 28 days prior to the first dose of CPX-POM and repeated at the end of every second cycle (i.e., at approximately 6-week intervals). During the Dose-Escalation Phase of the study, Screening cancer evaluations may be performed up to 28 days before Cycle 1, Day 1. For patients enrolled in any Expansion cohorts, Screening cancer evaluations must be performed within 28 days of Cycle 1, Day 1.
9. Hematology will include measurement of hemoglobin, hematocrit, platelets, RBC, reticulocytes, and WBC with differential. To shorten the duration of the Cycle 1, Day 1 visit, if needed, the safety laboratory blood samples required for this visit may be drawn up to 3 days before Day 1 (Cycle 1 only).
10. Clinical chemistry will include measurement of potassium, sodium, chloride, glucose, BUN, creatinine, creatinine clearance, ALT, AST, ALP, GGT, alkaline phosphatase, indirect bilirubin, direct bilirubin, total bilirubin, total protein, albumin, calcium, bicarbonate, magnesium, phosphate, lipase, and amylase. To shorten the duration of the Cycle 1, Day 1 visit, if needed, the safety laboratory blood samples required for this visit may be drawn up to 3 days before Day 1.
11. Thyroid panel will include TSH, free T4, and free and total T3 and will be repeated on D1 of each cycle.
12. Coagulation tests will include PT and aPTT and will be repeated on D1 of each cycle.
13. Urinalysis will include color, turbidity, pH, specific gravity, glucose, ketones, nitrites, bilirubin, urobilirubin, protein, RBCs, WBCs, epithelial cells, casts, crystals, and bacteria, and eGFR at Screening only.
14. A full physical examination will be conducted at Screening and at Follow-up. At each other study visit, patients will be assessed for continued dosing and any possible physical symptoms/toxicities and a physical examination may be performed, if indicated. Body weight should be measured at each study visit. Height should be measured at Screening.

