8. STUDY ASSESSMENTS

8.1. Cancer Evaluation

All patients will undergo a cancer evaluation to include determination of staging and metastases for screening purposes. Disease response assessments will be performed for patients with measurable disease within 28 days prior to the first dose of CPX-POM and repeated before the first study drug dose (Day 1) of every second cycle (i.e., at approximately 6-week intervals). If a patient with measurable disease discontinues from the study after 6 weeks and before a disease response assessment is scheduled, an additional assessment may be performed, upon consultation with the Sponsor, at the end of treatment (i.e., on approximately Day 22 of the last cycle).

For the screening assessments, all sites of disease will be imaged by CT, if possible. If the anatomic region cannot be adequately imaged by CT, magnetic resonance imaging (MRI) may be used instead. Subsequent assessments should use the same radiographic methods as used during Screening. Disease response will be assessed by the investigator using RECIST, version 1.1 (Eisenhauer et al, 2009; see Appendix 1). Tumor markers applicable to the patient's solid tumor type (e.g., prostate-specific antigen [PSA] for prostate cancer; cancer antigen-125 [CA-125] in ovarian cancer; carcinoembryonic antigen [CEA] in colorectal or pancreatic cancer, cancer antigen 19-9 [CA-19-9] in pancreatic cancer) will also be measured within ± 2 days of tumor measurements.

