Primary Tumor Site [n (%)]							
Primary Tumor Site #1	XX (XX.X)	XX (XX.X)	XX (XX.X)	XX (XX.X)	XX (XX.X)	XX (XX.X)	XX (XX.X)
Primary Tumor Site #2	XX (XX.X)	XX (XX.X)	XX (XX.X)	XX (XX.X)	XX (XX.X)	XX (XX.X)	XX (XX.X)
Primary Tumor Site #3	XX (XX.X)	XX (XX.X)	XX (XX.X)	XX (XX.X)	XX (XX.X)	XX (XX.X)	XX (XX.X)
<etc>							

Program: (Program name.sas) (run on: DDMMYYYY HH:MM)

Filename: (Specify file name.rtf)

PROGRAMMING NOTES:

- A last column with the header 'CPX-POM All Doses' will also be displayed.

Table 14.2.2 - Summary of Patients Responses
(Efficacy Population)

Visit/ Type of Response	CPX-POM 30 mg/m ² N=1	CPX-POM [D2] mg/m ² N=X	CPX-POM [D3] mg/m ² N=X	CPX-POM [D4] mg/m ² N=X	CPX-POM [D5] mg/m ² N=X	CPX-POM [D6] mg/m ² N=X	CPX-POM [D7] mg/m ² N=X
Cycle 2-Day 1 Visit							
Target Lesion Response [n (%)]							
Complete Response	XX (XX.X)	XX (XX.X)	XX (XX.X)	XX (XX.X)	XX (XX.X)	XX (XX.X)	XX (XX.X)
Partial Response	XX (XX.X)	XX (XX.X)	XX (XX.X)	XX (XX.X)	XX (XX.X)	XX (XX.X)	XX (XX.X)
Stable Disease	XX (XX.X)	XX (XX.X)	XX (XX.X)	XX (XX.X)	XX (XX.X)	XX (XX.X)	XX (XX.X)
Progressive Disease	XX (XX.X)	XX (XX.X)	XX (XX.X)	XX (XX.X)	XX (XX.X)	XX (XX.X)	XX (XX.X)
Not evaluable	XX (XX.X)	XX (XX.X)	XX (XX.X)	XX (XX.X)	XX (XX.X)	XX (XX.X)	XX (XX.X)
Non-Target Lesion Response [n (%)]							
Complete Response	XX (XX.X)	XX (XX.X)	XX (XX.X)	XX (XX.X)	XX (XX.X)	XX (XX.X)	XX (XX.X)
Partial Response	XX (XX.X)	XX (XX.X)	XX (XX.X)	XX (XX.X)	XX (XX.X)	XX (XX.X)	XX (XX.X)
Stable Disease	XX (XX.X)	XX (XX.X)	XX (XX.X)	XX (XX.X)	XX (XX.X)	XX (XX.X)	XX (XX.X)
Progressive Disease	XX (XX.X)	XX (XX.X)	XX (XX.X)	XX (XX.X)	XX (XX.X)	XX (XX.X)	XX (XX.X)
Not evaluable	XX (XX.X)	XX (XX.X)	XX (XX.X)	XX (XX.X)	XX (XX.X)	XX (XX.X)	XX (XX.X)
Overall Response [n (%)]							
Complete Response	XX (XX.X)	XX (XX.X)	XX (XX.X)	XX (XX.X)	XX (XX.X)	XX (XX.X)	XX (XX.X)
Partial Response	XX (XX.X)	XX (XX.X)	XX (XX.X)	XX (XX.X)	XX (XX.X)	XX (XX.X)	XX (XX.X)
Stable Disease	XX (XX.X)	XX (XX.X)	XX (XX.X)	XX (XX.X)	XX (XX.X)	XX (XX.X)	XX (XX.X)
Progressive Disease	XX (XX.X)	XX (XX.X)	XX (XX.X)	XX (XX.X)	XX (XX.X)	XX (XX.X)	XX (XX.X)
Not evaluable	XX (XX.X)	XX (XX.X)	XX (XX.X)	XX (XX.X)	XX (XX.X)	XX (XX.X)	XX (XX.X)

<repeat for Day 1 visit of each cycle from Cycle 3 to last Cycle number over all patients>

Program: (Program name.sas) (run on: DDMMYYYY HH:MM)

Filename: (Specify file name.rtf)

PROGRAMMING NOTES:

- A last column with the header 'CPX-POM All Doses' will also be displayed.

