Median	XX.X	XX.X	XX.X	XX.X	XX.X	XX.X	XX.X
Maximum	XX	XX	XX	XX	XX	XX	XX
Cycle 1-Day 4							
n	XX	XX	XX	XX	XX	XX	XX
Mean	XX.X	XX.X	XX.X	XX.X	XX.X	XX.X	XX.X
SD	XX.XX	XX.XX	XX.XX	XX.XX	XX.XX	XX.XX	XX.XX
Minimum	XX	XX	XX	XX	XX	XX	XX
Median	XX.X	XX.X	XX.X	XX.X	XX.X	XX.X	XX.X
Maximum	XX	XX	XX	XX	XX	XX	XX
Change from Baseline to Cycle 1-Day 4							
n	XX	XX	XX	XX	XX	XX	XX
Mean	XX.X	XX.X	XX.X	XX.X	XX.X	XX.X	XX.X
SD	XX.XX	XX.XX	XX.XX	XX.XX	XX.XX	XX.XX	XX.XX
Minimum	XX	XX	XX	XX	XX	XX	XX
Median	XX.X	XX.X	XX.X	XX.X	XX.X	XX.X	XX.X
Maximum	XX	XX	XX	XX	XX	XX	XX

<repeat for Cycle 1 Day 10 visit>
<for Cycle 2 to last-1 Cycle, repeat for Day 1 visit and Day 4 visit>
<for the last Cycle, repeat for Day 22 visit and Day 28 follow-up visit>

[a] Baseline was the last value/result of assessment prior to or on day of first study treatment.

Program: (Program name.sas) (run on: DDMMYYYY HH:MM)

Filename: (Specify file name.rtf)

PROGRAMMING NOTES:

- Repeat for all hematology parameters: Hemoglobin, Hematocrit, Platelet count, RBC count, Reticulocytes, WBC Count with Differential, Neutrophils, Lymphocytes, Monocytes, Eosinophils, Basophils.

Protocol: CPX-POM-001

--- DELIVERY TYPE ----

Page 1 of X

Table 14.3-2.1.2 - Outside of Normal Range - Shift Table for Hematology Laboratory Parameters
 (Safety Population)

Dose group : CPX-POM 30 mg/m² (N=1)

Parameter/ Visit	Value at Visit	Baseline [a] value				Total
		Low n (%)	Normal n (%)	High n (%)	Low/High* n (%)	
Hemoglobin (unit)						
Cycle 1-Day 4 (N**=XX)	Low	XX (XXX.X)	XX (XXX.X)	XX (XXX.X)	XX (XXX.X)	XX (XXX.X)
	Normal	XX (XXX.X)	XX (XXX.X)	XX (XXX.X)	XX (XXX.X)	XX (XXX.X)
	High	XX (XXX.X)	XX (XXX.X)	XX (XXX.X)	XX (XXX.X)	XX (XXX.X)
	Low/High*	XX (XXX.X)	XX (XXX.X)	XX (XXX.X)	XX (XXX.X)	XX (XXX.X)
	Total	XX (XXX.X)	XX (XXX.X)	XX (XXX.X)	XX (XXX.X)	XX
Cycle 1-Day 10 (N**=XX)	Low	XX (XXX.X)	XX (XXX.X)	XX (XXX.X)	XX (XXX.X)	XX (XXX.X)
	Normal	XX (XXX.X)	XX (XXX.X)	XX (XXX.X)	XX (XXX.X)	XX (XXX.X)
	High	XX (XXX.X)	XX (XXX.X)	XX (XXX.X)	XX (XXX.X)	XX (XXX.X)
	Low/High*	XX (XXX.X)	XX (XXX.X)	XX (XXX.X)	XX (XXX.X)	XX (XXX.X)
	Total	XX (XXX.X)	XX (XXX.X)	XX (XXX.X)	XX (XXX.X)	XX

<for Cycle 2 to last-1 Cycle, repeat for Day 1 visit and Day 4 visit>
 <for the last Cycle, repeat for Day 22 visit and Day 28 follow-up visit>
 <repeat for all doses groups>

Percentage was based on the number of patients present at each visit with non-missing results for the considered parameter.

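### SAP Table 14.2.2 has no end-of-treatment row and no best overall response, so a scan that ends treatment can go uncounted, depending on its visit label

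*SAP*

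**What the plan says.** **Response table.** SAP Table 14.2.2 opens with a block headed "Cycle 2-Day 1 Visit" and continues with "<repeat for Day 1 visit of each cycle from Cycle 3 to last Cycle number over all patients>". Each block gives target, non-target and overall response, and each of these includes a "Progressive Disease" row. No other visit block is specified.

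**Population.** The note to SAP Table 14.1-2 admits a treated patient to the efficacy population on two conditions: measurable disease at baseline and any later tumor assessment. It does not restrict the visit of that assessment.

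**Scheduled scans.** The protocol times them in two ways. Section 8.1 has them "repeated before the first study drug dose (Day 1) of every second cycle (i.e., at approximately 6-week intervals"). Table 1 footnote 8 has them "repeated at the end of every second cycle (i.e., at approximately 6-week intervals"). The Table 1 grid marks the cancer evaluation at Screening and D1 and leaves the D22 column empty.

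**Extra scan.** Section 8.1 allows one additional assessment, after consultation with the sponsor, for a patient with measurable disease who stops after 6 weeks and before a scan is due. It is placed "at the end of treatment (i.e., on approximately Day 22 of the last cycle").

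**Last visit.** Table 1 footnote 4 says: "If final treatment cycle, patient returns for assessments on Day 22". A patient who continues skips Day 22 and restarts at Day 1. Progression is one of the reasons for stopping treatment.

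**Other shells.** The laboratory tables do give the final cycle its own rows: "<for the last Cycle, repeat for Day 22 visit and Day 28 follow-up visit>".

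**The concern.** Day 22 and the next Day 1 are alternatives: a patient who stops attends the first, and a patient who continues attends the second. A response table built only on Day 1 visits has no place for an assessment recorded at a patient's last visit. Progression ends treatment, so the scans most exposed to this are those that show progression. The omission can therefore depend on the outcome.

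No other supplied output clearly fills the gap:

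- Table 14.2.1 only counts assessed patients by tumor site.
- Listings 16.2.4-6 and 16.2.4-7 give lesion diameters and non-target results, but have no column for overall response or new lesions.
- The disposition shell names no progression reason, although its programming note would let one appear.
- Protocol Section 8.2.1.1 keeps progression out of adverse event reporting.

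At stake is whether the table for this secondary objective accounts for every patient in its own N.

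**Working it through.** The plan states no figure on this point. The check compares visit structures, with calendar arithmetic on the 21-day cycle.

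**1. Calendar.** Day 22 of cycle k falls on study day 21(k − 1) + 22 = 21k + 1. Day 1 of cycle k + 1 falls on study day 21k + 1. For k = 2 both are study day 43 (week 6). For k = 4 both are study day 85 (week 12). One scan on one date can carry either label.

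**2. Where a treatment-ending scan lands.**

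| How the scan is filed | Basis in the protocol | Block in Table 14.2.2 |
|---|---|---|
| Pre-dose Day 1 of the next cycle | Section 8.1, Table 1 grid | Yes, and progression is counted even if no dose follows |
| End of the cycle, Day 22 | Table 1 footnotes 8 and 4 | None |
| Optional extra scan, about Day 22 of the last cycle | Section 8.1 | None |
| After the longest-treated patient's last cycle | Blocks stop at Day 1 of the highest cycle number | None, unless a Day 1 without dosing counts as a cycle |

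The shells contain no rule that assigns a scan to a visit. The first two rows can be the same scan.

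**3. Membership of N.** All four scans qualify a patient for the efficacy population. In the last three cases the patient is in N but the result is not tabulated. If that scan is the only post-baseline one, the patient appears in no response row. If there was an earlier scan, the table shows only the earlier result, and no best-overall-response row adds the later one.

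**4. Size, by illustration.** Assume 12 efficacy patients, of whom 30%, 50% or 70% progress at the week 6 scan, rounded to 4, 6 or 8 patients. These inputs are assumptions, not figures from the plan.

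| Progressors | Filed as Cycle 3 Day 1: progression shown | Filed as Cycle 2 Day 22: progression shown | Filed as Cycle 2 Day 22: all categories in the Cycle 3 Day 1 block |
|---|---|---|---|
| 4 | 4/12 = 33% | 0 | 8/12 = 67% of N |
| 6 | 6/12 = 50% | 0 | 6/12 = 50% of N |
| 8 | 8/12 = 67% | 0 | 4/12 = 33% of N |

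This is the extreme case, in which every progressor's scan is filed under Day 22. With N as denominator, the combined share with complete response, partial response or stable disease is the same under either label. Only the progression row changes, and 4 to 8 patients are left unaccounted for.

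**5. Size per cohort.** Standard cohorts have 3 to 6 patients. If all are evaluable, one lost progression is 1/3 = 33 to 1/6 = 17 percentage points of that dose column.

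**6. Would reconciling the scan timing be enough?** No. On the footnote 8 wording, treatment-ending scans filed at the end of a cycle still have no row. On the Section 8.1 wording, scheduled scans have a row, apart from the possible longest-treated exception, but the optional Day 22 scan does not. On the footnote 8 timing the first on-treatment scan falls at week 6, so the Cycle 2 Day 1 block would hold no scheduled scan.

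**The case against.** The strongest reply is that the table mirrors the schedule. Section 8.1 and the Table 1 grid tie scheduled scans to pre-dose Day 1. Every Day 1 block carries a progression row, which would have little use if only continuing patients could appear in it. The RECIST listings show baseline lesions under Cycle 1 Day 1 although baseline imaging belongs to Screening, which suggests that scans are filed under the following Day 1. This largely stands, and it is why the loss is conditional. The listing label does not settle the question, however. Every treated patient has a Cycle 1 Day 1, so it does not show where a scan that ends treatment is filed.

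Three further replies carry weight:

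- The Day 22 scan is optional and limited to a narrow group. That stands.
- The supplied SAP is the set of table shells and refers to SAP text outside them, where an assignment rule or best-response definition may exist. That stands as a caveat.
- The lesion data remain in listings that can be read by patient in a study of about 24. That stands in part, because overall response would have to be worked out by hand and the lesion listings show no new-lesion field.

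A reader might go further and infer that progressors systematically drop out and that disease control by dose is overstated. The documents do not support this. Scans filed under Day 1 are counted. The shell has no disease-control row. The only denominator it shows is the efficacy N, and on that N a missing progression does not raise the response or stable-disease rows. An inflated rate would need a denominator of patients present at each visit. Shells that use a visit-level denominator say so (Tables 14.3-2.1.2 and 14.3-3.2); Table 14.2.2 does not.

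**Conclusion.** The point holds as a structural gap in one table. As the shell is written, the optional end-of-treatment scan has no row. A treatment-ending scan has none if it is filed at the end of the cycle, or if it follows the longest-treated patient's last cycle. No best-overall-response summary makes up for this. The consequence is undercounted progression and patients in N whose result is not shown. It is not a demonstrated upward bias in disease control.

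The size depends on the visit label. It is nil for scheduled scans filed under an available Day 1 block. It is 17 to 33 percentage points of the progression row for each lost progression in a fully evaluable standard cohort. The conclusion assumes that no visit-assignment rule exists in SAP text outside the supplied shells. The change is worth making because the omission can depend on outcome and affects the only response table for a secondary objective.

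**What to change.** 1. In Table 14.2.2, add a block for end of treatment, covering Day 22 of the last cycle and unscheduled scans. Alternatively, tabulate by post-baseline assessment number (first, second and so on). Either way, state the rule that assigns scans to blocks, so that every post-baseline scan is counted once.
2. Add a best-overall-response summary with the efficacy N as denominator.
3. Reconcile the scan timing in Protocol Section 8.1 with Table 1 footnote 8.

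The cost is an edit to one table shell and a clarification of the protocol wording. No new data or scans are needed.

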1.3. Schedule of Assessments

The schedule of assessments is shown in Table 1.

Table 1. Schedule of Assessments

| Study Procedure | Screening Period | Treatment Period | | | | | | | | Follow-up Period ⁵ |
|---|---------------------------------|------------------|----|----|----|-----------------|----|------------------------------------|----------------------------------|---|
| | Study Days: D -28 to D -1 | D1 ¹ | D2 | D3 | D4 | D5 ¹ | D6 | D10 ² (Cycle 1 only) | D22 (last cycle) ⁴ | 28 (±5) days post last dose or at early termination |
| | Study Visits: V1 | V2 | V3 | V4 | V5 | V6 | V7 | V8 | | |
| Informed consent | X | | | | | | | | | |
| Inclusion/exclusion criteria | X | X | | | | | | | | |
| ECOG Performance Status | X | | | | | | | | | X |
| Medical history | X | | | | | | | | | |
| HIV and hepatitis screening ⁶ | X | | | | | | | | | |
| Pregnancy test ⁷ | X | X | | | | | | | | |
| Cancer evaluation ⁸ | X | X | | | | | | | | |
| CT or MRI | X | | | | | | | | | |
| MUGA or ECHO | X | | | | | | | | | |
| Hematology ⁹ | X | X | | | X | | | X | X | X |
| Clinical chemistry ¹⁰ | X | X | | | X | | | X | X | X |
| Thyroid panel ¹¹ | X | X | | | | | | | | |
| Coagulation test ¹² | X | X | | | | | | | | |
| Urinalysis ¹³ | X | X | | | | X | | X | X | X |
| Full physical exam ¹⁴ | X | | | | | | | | | X |
| Assess for physical symptoms/toxicities ¹⁵ | | X | X | X | X | X | X | X | X | |
| Ophthalmologic exam ¹⁵ | X | | | | | | | | | X |
| Vital signs ¹⁶ | X | X | X | X | X | X | X | X | X | X |
| ECG ¹⁷ | X | X | | | | X | | | | X |
| Start 24- hour Holter monitor ¹⁸ | | X | | | | | | | | |

| Study Procedure | Screening Period | Treatment Period | | | | | | | | Follow-up Period ⁵ |
|--|------------------|------------------|----|----|----|-----------------|----|---------------------------------|-------------------------------|---|
| | D -28 to D -1 | D1 ¹ | D2 | D3 | D4 | D5 ¹ | D6 | D10 ² (Cycle 1 only) | D22 (last cycle) ⁴ | 28 (±5) days post last dose or at early termination |
| Study Days: | V1 | V2 | V3 | V4 | V5 | V6 | V7 | V8 | | |
| Adverse events | X | X | X | X | X | X | X | X | X | X |
| Concomitant medications | X | X | X | X | X | X | X | X | X | X |
| PK blood samples ¹⁹ | | X | X | | | X | X | | | |
| PK urine samples ²⁰ | | X | X | | | X | X | | | |
| β glucuronidase urine sample ²¹ | | X | | | | X | | | | |
| Biomarker blood sample ²² | | X | | | | X | | | X | X |
| Body surface area ²³ | | X | | | | | | | | |

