> 150 bpm	XX (XXX.X)	XX (XXX.X)	XX (XXX.X)	XX (XXX.X)	XX (XXX.X)	XX (XXX.X)	XX (XXX.X)
[101-150] bpm	XX (XXX.X)	XX (XXX.X)	XX (XXX.X)	XX (XXX.X)	XX (XXX.X)	XX (XXX.X)	XX (XXX.X)
< 55 bpm	XX (XXX.X)	XX (XXX.X)	XX (XXX.X)	XX (XXX.X)	XX (XXX.X)	XX (XXX.X)	XX (XXX.X)
Cycle 1-Day 2 *							
> 150 bpm	XX (XXX.X)	XX (XXX.X)	XX (XXX.X)	XX (XXX.X)	XX (XXX.X)	XX (XXX.X)	XX (XXX.X)
[101-150] bpm	XX (XXX.X)	XX (XXX.X)	XX (XXX.X)	XX (XXX.X)	XX (XXX.X)	XX (XXX.X)	XX (XXX.X)
< 55 bpm	XX (XXX.X)	XX (XXX.X)	XX (XXX.X)	XX (XXX.X)	XX (XXX.X)	XX (XXX.X)	XX (XXX.X)

<repeat for next Cycle 1 visits>
<for Cycle 2 to last-1 Cycle, repeat for Day 1 visit to Day 6 visit>
<for the last Cycle, repeat for Day 1 visit to Day 6 visit, Day 22 visit and Day 28 follow-up visit>

* Denominator for the percentages.
[a] Baseline was the last value/result of assessment prior to or on day of first study treatment.
> 150 bpm: Very High values
[101-150] bpm: High values
< 55 bpm: Low values

Sponsor: CicloMed
Protocol: CPX-POM-001
Statistical Analysis Plan
(TFL shells):
Version 1.0 / 02FEB2018

Protocol: CPX-POM-001

--- DELIVERY TYPE ---

Page 2 of 3

Table 14.3-3.2 - Summary of Abnormal Vital Signs
(Safety Population)

Parameter/ Visit/ Category	CPX-POM 30 mg/m ² N=1	CPX-POM [D2] mg/m ² N=X	CPX-POM [D3] mg/m ² N=X	CPX-POM [D4] mg/m ² N=X	CPX-POM [D5] mg/m ² N=X	CPX-POM [D6] mg/m ² N=X	CPX-POM [D7] mg/m ² N=X
Systolic Blood Pressure (mmHg)							
Baseline [a]*	XX	XX	XX	XX	XX	XX	XX
>= 161 mmHg	XX (XXX.X)	XX (XXX.X)	XX (XXX.X)	XX (XXX.X)	XX (XXX.X)	XX (XXX.X)	XX (XXX.X)
[131-160] bpm	XX (XXX.X)	XX (XXX.X)	XX (XXX.X)	XX (XXX.X)	XX (XXX.X)	XX (XXX.X)	XX (XXX.X)
< 95 mmHg	XX (XXX.X)	XX (XXX.X)	XX (XXX.X)	XX (XXX.X)	XX (XXX.X)	XX (XXX.X)	XX (XXX.X)
Cycle 1-Day 2 *	XX	XX	XX	XX	XX	XX	XX
>= 161 mmHg	XX (XXX.X)	XX (XXX.X)	XX (XXX.X)	XX (XXX.X)	XX (XXX.X)	XX (XXX.X)	XX (XXX.X)
[131-160] bpm	XX (XXX.X)	XX (XXX.X)	XX (XXX.X)	XX (XXX.X)	XX (XXX.X)	XX (XXX.X)	XX (XXX.X)
< 95 mmHg	XX (XXX.X)	XX (XXX.X)	XX (XXX.X)	XX (XXX.X)	XX (XXX.X)	XX (XXX.X)	XX (XXX.X)

<repeat for next Cycle 1 visits>

<for Cycle 2 to last-1 Cycle, repeat for Day 1 visit to Day 6 visit>

<for the last Cycle, repeat for Day 1 visit to Day 6 visit, Day 22 visit and Day 28 follow-up visit>

* Denominator for the percentages.

[a] Baseline was the last value/result of assessment prior to or on day of first study treatment.

>= 161 bpm: Very High values

[131-160] bpm: High values

< 95 bpm: Low values

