Program: (Program name.sas) (run on: DDMMYYYY HH:MM)

Filename: (Specify file name.rtf)

Table 14.3-3.2 - Summary of Abnormal Vital Signs
 (Safety Population)

Parameter/ Visit/ Category	CPX-POM 30 mg/m ² N=1	CPX-POM [D2] mg/m ² N=X	CPX-POM [D3] mg/m ² N=X	CPX-POM [D4] mg/m ² N=X	CPX-POM [D5] mg/m ² N=X	CPX-POM [D6] mg/m ² N=X	CPX-POM [D7] mg/m ² N=X
Diastolic Blood Pressure (mmHg)							
Baseline [a]*	XX	XX	XX	XX	XX	XX	XX
>= 101 mmHg	XX (XXX.X)	XX (XXX.X)	XX (XXX.X)	XX (XXX.X)	XX (XXX.X)	XX (XXX.X)	XX (XXX.X)
[86-100] bpm	XX (XXX.X)	XX (XXX.X)	XX (XXX.X)	XX (XXX.X)	XX (XXX.X)	XX (XXX.X)	XX (XXX.X)
< 50 mmHg	XX (XXX.X)	XX (XXX.X)	XX (XXX.X)	XX (XXX.X)	XX (XXX.X)	XX (XXX.X)	XX (XXX.X)
Cycle 1-Day 2 *	XX	XX	XX	XX	XX	XX	XX
>= 101 mmHg	XX (XXX.X)	XX (XXX.X)	XX (XXX.X)	XX (XXX.X)	XX (XXX.X)	XX (XXX.X)	XX (XXX.X)
[86-100] bpm	XX (XXX.X)	XX (XXX.X)	XX (XXX.X)	XX (XXX.X)	XX (XXX.X)	XX (XXX.X)	XX (XXX.X)
< 50 mmHg	XX (XXX.X)	XX (XXX.X)	XX (XXX.X)	XX (XXX.X)	XX (XXX.X)	XX (XXX.X)	XX (XXX.X)

<repeat for next Cycle 1 visits>

<for Cycle 2 to last-1 Cycle, repeat for Day 1 visit to Day 6 visit>

<for the last Cycle, repeat for Day 1 visit to Day 6 visit, Day 22 visit and Day 28 follow-up visit>

* Denominator for the percentages.

[a] Baseline was the last value/result of assessment prior to or on day of first study treatment.

>= 101 bpm: Very High values

[86-100] bpm: High values

< 50 bpm: Low values

Program: (Program name.sas) (run on: DDMMYYYY HH:MM)

Filename: (Specify file name.rtf)

Sponsor: CicloMed
Protocol: CPX-POM-001
Statistical Analysis Plan
(TFL shells):
Version 1.0 / 02FEB2018

Table 14.3-4.1 - Summary of ECG Parameters
(Safety Population)

Replicate of Table 14.3-2.1.1

PROGRAMMING NOTES:

- Update "laboratory parameter" by "ECG parameter"
- Include all ECG parameters

Table 14.3-4.2 - Summary of Abnormal ECG Intervals
 (Safety Population)

Parameter/ Visit/ Category	CPX-POM 30 mg/m ² N=1	CPX-POM [D2] mg/m ² N=X	CPX-POM [D3] mg/m ² N=X	CPX-POM [D4] mg/m ² N=X	CPX-POM [D5] mg/m ² N=X	CPX-POM [D6] mg/m ² N=X	CPX-POM [D7] mg/m ² N=X
Heart rate (bpm)							
Baseline [a]*	XX	XX	XX	XX	XX	XX	XX
Normal	XX (XXX.X)	XX (XXX.X)	XX (XXX.X)	XX (XXX.X)	XX (XXX.X)	XX (XXX.X)	XX (XXX.X)
Abnormal, NCS	XX (XXX.X)	XX (XXX.X)	XX (XXX.X)	XX (XXX.X)	XX (XXX.X)	XX (XXX.X)	XX (XXX.X)
Abnormal, CS	XX (XXX.X)	XX (XXX.X)	XX (XXX.X)	XX (XXX.X)	XX (XXX.X)	XX (XXX.X)	XX (XXX.X)
Cycle 1-Day 5 *	XX	XX	XX	XX	XX	XX	XX

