Normal	XX (XXX.X)	XX (XXX.X)	XX (XXX.X)	XX (XXX.X)	XX (XXX.X)	XX (XXX.X)	XX (XXX.X)
Abnormal, NCS	XX (XXX.X)	XX (XXX.X)	XX (XXX.X)	XX (XXX.X)	XX (XXX.X)	XX (XXX.X)	XX (XXX.X)
Abnormal, CS	XX (XXX.X)	XX (XXX.X)	XX (XXX.X)	XX (XXX.X)	XX (XXX.X)	XX (XXX.X)	XX (XXX.X)

<for Cycle 2 to last-1 cycle, repeat for Day 1 visit>
 <for last cycle, repeat for Day 1 visit and Day 28 follow-up visit>
 <repeat for PR interval and QRS interval>

* Denominator for the percentages.

[a] Baseline was the last value/result of assessment prior to or on day of first study treatment.

CS = Clinically Significant; NCS = Not Clinically Significant.

Program: (Program name.sas) (run on: DDMMYYYY HH:MM)

Filename: (Specify file name.rtf)

Table 14.3-4.2 - Summary of Abnormal ECG Intervals
 (Safety Population)

Parameter/ Visit/ Category	CPX-POM 30 mg/m ² N=1	CPX-POM [D2] mg/m ² N=X	CPX-POM [D3] mg/m ² N=X	CPX-POM [D4] mg/m ² N=X	CPX-POM [D5] mg/m ² N=X	CPX-POM [D6] mg/m ² N=X	CPX-POM [D7] mg/m ² N=X
QTcB interval (msec)							
Baseline [a] *	XX	XX	XX	XX	XX	XX	XX
> 450 msec	XX (XXX.X)	XX (XXX.X)	XX (XXX.X)	XX (XXX.X)	XX (XXX.X)	XX (XXX.X)	XX (XXX.X)
> 480 msec	XX (XXX.X)	XX (XXX.X)	XX (XXX.X)	XX (XXX.X)	XX (XXX.X)	XX (XXX.X)	XX (XXX.X)
> 500 msec	XX (XXX.X)	XX (XXX.X)	XX (XXX.X)	XX (XXX.X)	XX (XXX.X)	XX (XXX.X)	XX (XXX.X)
Cycle 1-Day 5 *	XX	XX	XX	XX	XX	XX	XX
> 450 msec	XX (XXX.X)	XX (XXX.X)	XX (XXX.X)	XX (XXX.X)	XX (XXX.X)	XX (XXX.X)	XX (XXX.X)
> 480 msec	XX (XXX.X)	XX (XXX.X)	XX (XXX.X)	XX (XXX.X)	XX (XXX.X)	XX (XXX.X)	XX (XXX.X)
> 500 msec	XX (XXX.X)	XX (XXX.X)	XX (XXX.X)	XX (XXX.X)	XX (XXX.X)	XX (XXX.X)	XX (XXX.X)
Change from Baseline to Cycle 1-Day 5 *	XX	XX	XX	XX	XX	XX	XX
> 30 msec	XX (XXX.X)	XX (XXX.X)	XX (XXX.X)	XX (XXX.X)	XX (XXX.X)	XX (XXX.X)	XX (XXX.X)
> 60 msec	XX (XXX.X)	XX (XXX.X)	XX (XXX.X)	XX (XXX.X)	XX (XXX.X)	XX (XXX.X)	XX (XXX.X)
<for Cycle 2 to last-1 cycle, repeat for Day 1 visit>							
<for last cycle, repeat for Day 28 follow-up visit>							
<repeat for QTcF interval>							

* Denominator for the percentages.

[a] Baseline was the last value/result of assessment prior to or on day of first study treatment.

CS = Clinically Significant; NCS = Not Clinically Significant.

Program: (Program name.sas) (run on: DDMMYYYY HH:MM)

Filename: (Specify file name.rtf)

PROGRAMMING NOTES: For QTcF interval, the category '> 500 msec' will be replaced by '> 500 msec (CS)' and the category '> 60 msec' will be replaced by '> 60 msec (CS)'.

Sponsor: CicloMed

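### Visit rows in the SAP shells for laboratory values, vital signs and ECG do not match the protocol schedule, mainly because the last cycle has no on-treatment rows

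*SAP*

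**What the plan says.** **Laboratory shells.** SAP Table 14.3-2.1.1 (hematology by visit) shows baseline and Cycle 1 Day 4, then gives three instructions: "repeat for Cycle 1 Day 10 visit", "for Cycle 2 to last-1 Cycle, repeat for Day 1 visit and Day 4 visit" and "for the last Cycle, repeat for Day 22 visit and Day 28 follow-up visit". The normal-range and clinician-assessment shift tables (14.3-2.1.2 and 14.3-2.1.3) have the same rows. The chemistry tables (14.3-2.2.1 to 2.2.3) replicate them unchanged. The urinalysis tables (14.3-2.5.1 to 2.5.3) replicate them with Day 5 in place of Day 4. Coagulation and thyroid are overridden to Day 1 of each cycle.

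**Vital signs.** Table 14.3-3.1 replicates 14.3-2.1.1. Its notes list the parameters and recall the within-day timing on Days 1 and 5, but state no last-cycle rows. Table 14.3-3.2 (abnormal values) does: "for the last Cycle, repeat for Day 1 visit to Day 6 visit, Day 22 visit and Day 28 follow-up visit".

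**ECG.** In Table 14.3-4.2 both blocks have a Cycle 1 Day 5 row. For heart rate, PR and QRS the shell then says "for last cycle, repeat for Day 1 visit and Day 28 follow-up visit". For QTcB and QTcF it says only "for last cycle, repeat for Day 28 follow-up visit". Table 14.3-4.1 is a replicate of 14.3-2.1.1. Its notes change the parameter label and add "Include all ECG parameters", with nothing on visits.

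**Protocol.** The hematology row of Table 1 reads "Hematology ⁹ | X | X | | | X | | | X | X | X": screening, D1, D4, D10 (Cycle 1 only), D22 (last cycle) and follow-up. Chemistry is the same; urinalysis has D5 instead of D4. Under footnote 4, a patient who continues skips Day 22 and begins again at Day 1. Under footnote 17, ECGs after screening are taken on Days 1 and 5 of Cycle 1, on Day 1 of each later cycle, and at the final visit.

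**The concern.** Protocol section 9.5.4 promises laboratory values and changes from baseline by dose group and makes no exception for the last cycle. Followed literally, the shells give no place to the Day 1 and Day 4 results of a last cycle numbered 2 or higher.

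Protocol section 4.1 lists progression, intolerable toxicity and other withdrawal criteria as reasons to stop. If the last cycle means the patient's own, the untabulated values come from the cycle in which that patient stopped. The Cycle k rows (k≥2) then hold only patients who went on to Cycle k+1. By-visit means and shifts would be conditioned on continuing, which can bias them.

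The ECG shells raise a separate question: whether the planned rows are the days on which ECGs are taken at all.

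**Working it through.** The plan states no figure here, so the check sets scheduled post-baseline visits against the rows each shell produces. K is a patient's number of cycles. The documents do not give it, so a range is shown. Cycle 1 Day 1 is not counted, because the SAP's baseline is the last value on or before the first treatment day. The last cycle is first read as the patient's own.

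**Hematology and chemistry**
- Scheduled: Cycle 1 D4 and D10 (2), plus D1 and D4 of Cycles 2 to K, 2(K−1), plus D22 and follow-up (2). Total 2K+2.
- Rows for K≥2: 2, plus 2(K−2), plus 2. Total 2K.
- Without a row: 2, always last-cycle D1 and D4. For K=1 all 4 of 4 have a row.
- Urinalysis gives the same count with D5 for D4.

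**ECG**
- Scheduled: Cycle 1 D5, D1 of Cycles 2 to K, and follow-up. Total K+1.
- Table 14.3-4.2, heart rate/PR/QRS: none missing. QTcB/QTcF: last-cycle D1 missing for K≥2.
- Table 14.3-4.1 for K≥2: Cycle 1 D5 and last-cycle D1 missing. Rows without a scheduled ECG are Cycle 1 D4, Cycle 1 D10, D4 of Cycles 2 to K−1, and D22: 3 + (K−2) = K+1. For K=1: Cycle 1 D5 missing and 3 such rows.

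| K | Lab sets scheduled | Lab sets with no row | ECGs scheduled | QTc block of 14.3-4.2: no row | 14.3-4.1: no row | 14.3-4.1: rows without an ECG |
|---|---|---|---|---|---|---|
| 1 | 4 | 0 | 2 | 0 | 1 | 3 |
| 2 | 6 | 2 (33%) | 3 | 1 | 2 | 3 |
| 3 | 8 | 2 (25%) | 4 | 1 | 2 | 4 |
| 4 | 10 | 2 (20%) | 5 | 1 | 2 | 5 |
| 6 | 14 | 2 (14%) | 7 | 1 | 2 | 7 |

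**Which last cycle?** Protocol footnote 4 is patient-specific, since Day 22 belongs to that patient's final cycle. SAP Table 14.2.2 runs to the highest cycle over all patients, which is study-wide. Footnote [b] of SAP Table 14.1-1 mixes the two. Its block of rows ends one cycle before the last, yet it provides for patients whose own last cycle falls inside that block.

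**Study-wide reading.** Rows for Cycle k below the study maximum hold everyone treated in Cycle k, so the selection and the per-patient shares above do not arise. Only the highest cycle number lacks D1 and D4. But the Day 22 and follow-up rows then belong to that cycle, and patients who stopped earlier have no clear row for those two visits.

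**The case against.** The strongest reply is that the study-wide reading is the intended one. Footnote [b] of Table 14.1-1 and the wording of Table 14.2.2 support it, and it removes the selection argument. That stands as far as it goes: the documents do not establish that each Cycle k row is restricted to patients who continued. It does not clear the shells, because it moves the gap to Day 22 and follow-up of earlier stoppers.

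It can also be said that the intent was additive. The hematology, vital-signs and ECG listings add the end-of-treatment visits to the earlier ones. This makes an oversight more likely than a choice, but the tables as written do not say it.

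Other points stand and limit the issue:
- Cycle 1, the DLT window, has fixed Day 4 and Day 10 rows, so a patient treated only in Cycle 1 loses no on-treatment laboratory row on either reading.
- Coagulation, thyroid, Table 14.3-3.2 and the heart rate/PR/QRS block keep their last-cycle visits.
- The Cycle 1 Day 5 ECG is missing from 14.3-4.1 only; 14.3-4.2 and the ECG listing show it. This is a schedule mismatch, not a last-cycle loss.
- Worst-grade tables and listings retain the values, and clinically significant laboratory results are also recorded as AEs (Protocol 8.2.3.6). The laboratory summaries are descriptive, and cohorts have 1 to 6 patients.
- The SAP document is headed as TFL shells and refers to the SAP for its vital-sign flags. Visit rules may exist in text not available here. Explicit shell instructions should still agree with them.

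**Conclusion.** The shells are wrong as written. Three mismatches with the protocol schedule are certain from the text:

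1. Tables 14.3-2.1.1 to 2.1.3, their chemistry and urinalysis replicates, and Table 14.3-3.1 have no on-treatment rows for a last cycle numbered 2 or higher.
2. The QTc block of 14.3-4.2 omits a last-cycle Day 1 that the companion block keeps.
3. Table 14.3-4.1 has rows on days without an ECG and lacks Cycle 1 Day 5.

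The size of the first depends on an undefined term. On the patient-specific reading it is 2 of 2K+2 sets for each patient with K≥2, assuming all scheduled visits are attended: 33% at K=2, falling to 14% at K=6. On the study-wide reading it is the highest cycle number only, plus an unclear place for Day 22 and follow-up of earlier stoppers.

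A reader might infer that toxicity in the stopping cycle is hidden, or that laboratory safety is made to look better. The documents do not support that. They give neither the number of cycles per patient nor how often toxicity is the reason for stopping, and one of the two readings involves no selection. Bias is possible, but its direction and size cannot be derived. The effect is on visit-level means and shifts, not on detection of the worst toxicity or on the MTD, which rests on DLTs.

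**What to change.** - Define the last cycle once and use it in one sense throughout.
- In Tables 14.3-2.1.1 to 2.1.3 and the chemistry and urinalysis replicates, show Day 1 and Day 4 (Day 5 for urinalysis) by cycle number for all patients treated in that cycle, including their last. Put Day 22 and follow-up in separate end-of-treatment rows. All 2K+2 scheduled sets then have a row.
- In Table 14.3-3.1, list the scheduled vital-sign days in the same way, as 14.3-3.2 already does for the last cycle.
- In Table 14.3-4.2, add last-cycle Day 1 to the QTcB/QTcF block.
- Give Table 14.3-4.1 its own visit list: baseline, Cycle 1 Day 5, Day 1 of each later cycle, and follow-up. This covers all K+1 scheduled post-baseline ECGs and leaves no empty rows.

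The cost is shell wording and programming. No new data, visits or protocol change are needed.
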